#### 2. GOALS

The study has 3 objectives:

- 1. To find out if the clinical impact of traditional and 3D printed lower leg orthoses differs
- 2. To evaluate patient satisfaction with traditional and 3D printed lower leg orthoses

3. To inventory the cost of 3D printed lower leg orthoses, and to evaluate the impact of the implementation of the new sizing and production workflow

#### 3. STUDY DESIGN

A member of staff from the local orthopaedic centre will go through the information and consent form with the test subject and submit it for signing.

Within the research project 3 main groups of treatments will be investigated:

- orthoses for patients with drop foot and knee instability that are used while walking (further mentioned as dynamic orthoses)

- night splints (static orthoses) for genu varum and foot stance deformities (e.g. talipes equinus, talipes valgus)

- seating shells for children with e.g. CP

For all target groups, patients are recruited separately and checked for specific outcome measures.

The first group are patients who wear their orthosis to move around. There is primarily an immediate effect (the effect of wearing the orthosis) and less of a therapeutic effect (which improves the patient in the long term).

The second group of patients wear the orthosis at night to reduce ankle or knee joint deformity. Here, the therapeutic effect is particularly important; the orthosis helps to correct the position of the foot or leg with a lasting effect.

#### **Dynamic ortheses**

The primary outcome measure here is the measured speed in the 10 metre walk test (10MWT), in metres per second. A secondary outcome measure is patient satisfaction, measured using the OPUS/CSD scale (Orthotics and Prosthetics Users' Survey - Satisfaction with Devices) [6], which surveys patient satisfaction with the orthosis.

Patients meeting the inclusion and exclusion criteria are recruited from existing patient lists. The patients are all already wearing dynamic orthoses.

The patients will be fitted with both a new traditional orthosis and a new 3D printed orthosis. The study is designed so that all patients are fitted with both types of orthosis in a crossover design [3].

The 2 conditions included and patients recruited also give rise to 2 different types of orthoses: an ankle-foot orthosis (AFO) for the drop foot patients, and a knee-ankle-foot orthosis (KAFO) for the patients with knee instability.

Patients are measured while wearing the orthosis, and while not wearing the orthosis (3 times each, and in a randomised order). The first baseline measurement is taken at the start of the measurement campaign (T0). For each type of orthosis, the patient is given 3 weeks to walk with the orthosis before being checked for a new measurement. After the first phase with the first orthosis (traditional or 3D printed), the patient is measured again (T1), with and without the orthosis. After the second phase with the second orthosis (3D-printed or traditional), the patient will be measured again (T2), with and without the orthosis.

The statistical analysis will be done with repeated measures analyses of variance (RM-ANOVA's), with the 2 within-subject factors: the 2 phases (phase 1 and phase 2), and the wearing or not of the orthosis (with and without), and 2 between-subject factors: the orthosis/pathology (AFO for drop foot, KAFO for knee instability), the treatment group (group A and group B).Sample size

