#### Sample size

As indicated above, the primary outcome measure is the measured speed during the 10m walk test. A secondary outcome measure here is patient satisfaction, calculated from the OPUS-CSD scale. Our sample size is not adjusted for multiple testing.

The sample size was calculated based on an effect size estimate of 25%, and an  $\alpha$  equal to 5%, and a power of 80% ( $\beta$  = 0.20). In total, there are 4 groups (2 between-subject factors with 2 levels each), and we compare at 2 measurement points, T1 and T2. We expect that measured patient parameters (the speed) do not change that much over time and with the orthosis, so we take a correlation of 0.6.

This gives a total of 40 patients, or 10 patients per group. With a margin of 20% for drop-out, we arrive at 12 patients per group (total of 48).

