#### 4. PATIENT SELECTION

The recruitment of the maximum of 105 subjects will be done on the one hand by contacting patients who are already in the contact details of the orthopaedic centres involved, and this specifically for patients who will be fitted with the dynamic orthoses. On the other hand, the patients receiving the night splint will be new patients.

Patients and parents of patients in this second target group will be given information about the research project by means of a visual information sheet when they check in at the centre. The doctor or staff member will inform the patient and parents in detail about the research project. They can then decide whether or not to take part in the study.

The patients from the first target group will be contacted by a staff member of the centre who will explain the research project. The patient has the time to make a voluntary decision whether or not to take part in the research project. If the patient is interested in participating, he/she is invited to come to the centre, where the visual information sheet will explain the project once more. The information and consent form will be presented for signing before entering the project.

Patient selection Patients with foot stance deformities - Inclusion o Age: >= 2 years, <= 6 years Gender: any gender Pathology: foot stance deformity o Unilateral as well as bilateral orthoses were included - Exclusion o Patient is already wearing a night splint Patients with genu varum - Inclusion Age: >= 2 years, <= 6 years Gender: any gender Pathology: genu varum o Both unilateral and bilateral orthoses are included - Exclusion o Patient is already wearing a night splint o The patient cannot stand upright

Patients with drop foot

- Inclusion

Age: >= 18 years

Gender: any gender Pathology: drop foot Patient is already wearing foot orthosis for drop foot Patient is able to walk at least 10 meters with or without the assistance of an aid (such as a cane) - Exclusion Wearing bilateral orthosis Wearing other orthosis (such as corset) Having a mental disorder The patient is pregnant Patients with knee instability - Inclusion o Age: >= 18 years Gender: any Pathology: knee instability Patient is already wearing an orthosis for knee instability Patient is able to walk at least 10 meters with or without the aid of an aid (such as a cane) - Exclusion Wearing a bilateral orthosis Having a mental disorder, neurological disorder o The patient is pregnant

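### The RM-ANOVA fixed for the dynamic orthoses discards patients who have valid with-orthosis speeds on both devices but no walk without the orthosis; a mixed model on with-orthosis speed would keep them

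*Protocol*

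**What the plan says.** Protocol section 3, on dynamic orthoses, names the method: "The statistical analysis will be done with repeated measures analyses of variance". The within-subject factors are "the 2 phases (phase 1 and phase 2), and the wearing or not of the orthosis (with and without"; the between-subject factors are orthosis/pathology and treatment group. Device is not itself a factor, so its effect is carried by phase by treatment group.

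On measurement, the same section says: "Patients are measured while wearing the orthosis, and while not wearing the orthosis (3 times each, and in a randomised order". Both conditions are repeated at T1 and T2.

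The sample size paragraph for this group says "In total, there are 4 groups (2 between-subject factors with 2 levels each), and we compare at 2 measurement points, T1 and T2" and allows for losses: "With a margin of 20% for drop-out, we arrive at 12 patients per group (total of 48".

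The walking criterion in section 4, for both drop foot and knee instability, is: "Patient is able to walk at least 10 meters with or without the assistance of an aid (such as a cane". The aid given as an example is a cane. Nothing asks for 10 m without the orthosis. Every patient in this group already wears one.

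**The concern.** Two phases by two wearing conditions give four cells per patient. Conventional RM-ANOVA deletes a patient with any empty cell. Two routes to an empty cell can be foreseen from the protocol:

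- **No T2 visit.** The plan itself allows for 20% drop-out.
- **No walk without the orthosis.** An orthosis-dependent patient is eligible but may be unable to supply these cells.

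The second route is the more awkward. The patient may have with-orthosis speeds on both devices, which is what the device question needs, and is removed for lack of a measurement that question does not use. Those removed would be the most orthosis-dependent. On the first route, complete-case analysis can also bias the device difference if leaving after phase 1 depends on how well the patient walked and does so unequally between the two orders.

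**Working it through.** **1. The plan's own figure.** The protocol says: "The sample size was calculated based on an effect size estimate of 25" percent. I read this as Cohen's f = 0.25, an assumption that returns the stated number. The other inputs are alpha 0.05, k = 4 groups, m = 2 times and rho = 0.6.

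- Noncentrality: lambda = f² N m / (1 - rho) = 0.0625 × N × 2 / 0.4 = 0.3125 N.
- For the group-by-time interaction, df = (k - 1)(m - 1) = 3 and (N - k)(m - 1) = N - 4.
- At N = 40, lambda = 12.5 and power is 0.812. This is the smallest N reaching 0.80, so the stated 40 is reproduced.

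**2. Loss of complete cases.** Let u be the share of KAFO patients unable to walk without the orthosis. The documents give no figure, so u = 0 to 0.4 is assumed. KAFO patients number 2 × 12 = 24, and complete cases are (48 - 24u) × 0.8. The device contrast (phase by treatment group) has 1 df; the same f and rho are applied to it.

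| u | Complete cases | lambda | Power, 3-df interaction | Power, 1-df device contrast |
|---|---|---|---|---|
| 0 | 38.4 | 12.0 | 0.79 | 0.92 |
| 0.1 | 36.5 | 11.4 | 0.77 | 0.91 |
| 0.2 | 34.6 | 10.8 | 0.74 | 0.89 |
| 0.3 | 32.6 | 10.2 | 0.71 | 0.87 |
| 0.4 | 30.7 | 9.6 | 0.67 | 0.85 |

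A model for with-orthosis speed alone recovers all the patients lost by this route. If 8 of 48 could not do the bare walk and nobody dropped out, the device contrast would rest on 40 patients under RM-ANOVA and 48 under the mixed model.

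**3. Precision for patients missing T2.** Take 24 patients per order, of whom 19 complete (38 completers and 10 with phase 1 only), unit variance and rho = 0.6.

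- Complete cases: ½ × 2(1 - rho)/19 = 0.4/19 = 0.0211.
- Likelihood, with-orthosis data only: ½ × [(1 - rho)²/24 + (1 - rho²)/19] = ½ × (0.00667 + 0.03368) = 0.0202, about 4% lower.
- With 8 patients missing T2 and the bare walks also in the model, the variances are 0.01896 and 0.02000, about 5% lower.

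**4. Complete-case bias.** Suppose the lowest share q of phase-1 walkers leaves within each order. The mean phase-1 speed of those who remain is then shifted up by h(q) = φ(z_q)/(1 - q) SD, and their phase-2 speed by rho × h(q). The bias in printed minus traditional is ½(1 - rho)[h(q printed-first) - h(q traditional-first)].

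| Drop-out, printed-first / traditional-first | h values | Bias (SD) |
|---|---|---|
| 20% / 20% | 0.350, 0.350 | 0 |
| 25% / 15% | 0.424, 0.274 | 0.2 × 0.150 = 0.03 |
| 30% / 10% | 0.497, 0.195 | 0.2 × 0.302 = 0.06 |

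A large simulation gave the same values. At 30%/10% a true difference of -0.30 SD appears as -0.24. The likelihood estimate was unbiased in every case, because drop-out depended only on observed speeds.

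**5. A trap in the replacement model.** There are three walks per condition and visit. If single walks are modelled with only a random patient effect, walks within a visit are treated as no more alike than walks at different visits. Assume between-visit correlation 0.6 and within-visit correlation w, and let B = (1 + 2w)/3 - 0.6.

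- True variance of a patient's visit-mean difference: 2B. Variance the model uses: (2/3) × [4(1 - w) + 3B]/5.
- w = 0.7: B = 0.200, so 0.400 against 0.240. The standard error is too small by a factor of 1.29, and type I error is about 0.13.
- w = 0.9: B = 0.333, so 0.667 against 0.187. The factor is 1.89, and type I error is about 0.30.

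Hence the walks should be averaged first, or a patient-by-visit random effect added.

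**The case against.** **The power loss is small for the question asked.** A reader might infer that the device comparison falls from 79% to 67% power. It does not: those figures belong to the 3-df interaction. The device contrast stays above 0.80 throughout the assumed range. This stands.

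**The bare-walk failure rate has no source.** Section 4 excludes bilateral orthosis wearers from both groups and neurological disorder from the knee-instability group, the test is only 10 m, and a cane is allowed. Three walks per condition mean that one failed attempt need not empty a cell. This stands, so the size is a range under assumption.

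**Losing these patients need not bias the device contrast.** If the inability is a stable trait present before either study device, it narrows the population but favours neither device within patients. This stands. The drop-out bias likewise needs unequal performance-related leaving between orders, which the protocol nowhere indicates. A reader might infer that the planned result will be biased; the documents do not support that.

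**RM-ANOVA is an accepted crossover analysis, and missing-data rules usually belong in the SAP.** Partly right. The protocol does not prescribe listwise deletion, it speaks of analyses in the plural, and the SAP is not shown. The absence of a missing-data rule is therefore not the point. What remains is that the protocol fixes a method and factor structure that, run in the usual way, require all four cells, when a better method needs no extra data.

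**The with/without comparison is of interest in itself**, since section 3 names the immediate effect of wearing the orthosis for this group. It can be kept as a separate analysis.

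**Conclusion.** The point holds at moderate weight, for the dynamic orthoses only. As conventionally run, the stated RM-ANOVA removes patients whose with-orthosis data on both devices are complete, and the eligibility text leaves room for such patients.

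Under the assumed 10% to 40% of KAFO patients, the cost is about 2 to 8 complete cases beyond drop-out (38.4 - 36.5 = 1.9; 38.4 - 30.7 = 7.7). Device-contrast power falls by 0.01 to 0.07, and the power of the interaction used for sizing by 0.02 to 0.12. The 20% margin is for drop-out and makes no separate provision for missing bare walks. For T2 drop-out the gain is mainly validity under missing-at-random rather than precision.

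These sizes rest on f = 0.25, rho = 0.6, the assumed failure range and the illustrative drop-out patterns.

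A reader might extend the point to the night splints. The documents do not support that: those patients are measured only without the orthosis, so there are no worn and unworn cells, and section 3 describes a lasting effect there.

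**What to change.** For the dynamic orthoses, replace the RM-ANOVA wording as follows:

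- Average the three walks per condition and visit.
- Fit a linear mixed model to all available with-orthosis means at T1 and T2, with fixed effects for device, phase, treatment order, pathology and device by pathology, and a random patient effect. If single walks are modelled instead, add a patient-by-visit random effect.
- Make printed minus traditional with-orthosis speed the primary contrast.
- Analyse the with/without comparison separately, so that a missing bare walk does not remove the patient from the device comparison.

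The cost is a change of analysis wording and slightly more analysis work in standard software, with no new patients, visits or measurements. The model relies on missing-at-random, which should be stated; it is a weaker condition than complete-case RM-ANOVA needs. The night-splint analysis should be specified on its own terms, with the T0 value and lasting effects addressed there.

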#### Sample size

As indicated above, the primary outcome measure is the measured speed during the 10m walk test. A secondary outcome measure here is patient satisfaction, calculated from the OPUS-CSD scale. Our sample size is not adjusted for multiple testing.

The sample size was calculated based on an effect size estimate of 25%, and an  $\alpha$  equal to 5%, and a power of 80% ( $\beta$  = 0.20). In total, there are 4 groups (2 between-subject factors with 2 levels each), and we compare at 2 measurement points, T1 and T2. We expect that measured patient parameters (the speed) do not change that much over time and with the orthosis, so we take a correlation of 0.6.

This gives a total of 40 patients, or 10 patients per group. With a margin of 20% for drop-out, we arrive at 12 patients per group (total of 48).

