#### Sample size

Here, the primary outcome measure is the measured angle of the ankle or knee. A secondary outcome measure here is patient satisfaction, calculated from the OPUS-CSD scale and measured ROM. Our sample size is not adjusted for multiple testing.

The calculation of the sample size is similar to that of the first patient group. However, there are now 3 moments where we will compare the angles (T0, T1, T2), and a lower value for the correlation is expected, since an influence of the treatment is expected, and the correlation at successive measurements may be smaller. The correlation is estimated here at 0.4. This gives a patient number of 12 per group (48 in total).

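### The 48 dynamic-orthosis patients cover 16.7% drop-out, not 20%: 40 was multiplied by 1.2 instead of divided by 0.8; the night-splint 48 appears to carry no margin

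*Protocol*

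**What the plan says.** The Sample size section under Dynamic ortheses takes an effect size of 25%, α of 5%, power of 80% and this layout: "In total, there are 4 groups (2 between-subject factors with 2 levels each), and we compare at 2 measurement points, T1 and T2". On the repeated measurements it adds: "so we take a correlation of 0.6". The result is "This gives a total of 40 patients, or 10 patients per group". The next sentence raises it: "With a margin of 20% for drop-out, we arrive at 12 patients per group (total of 48").

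The Sample size section under Night splints describes its calculation as similar, with two changes. The number of time points rises: "there are now 3 moments where we will compare the angles (T0, T1, T2"). The correlation falls to 0.4. Its result is "This gives a patient number of 12 per group (48 in total"). It mentions no drop-out margin and does not say whether 48 is before or after drop-out.

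Section 4 sets an overall ceiling: "The recruitment of the maximum of 105 subjects". Section 1 also speaks of up to 105.

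**The concern.** A drop-out allowance should leave the required number once the stated fraction of enrolled patients has been lost. That means dividing the required number by (1 − d). Multiplying by (1 + d) always gives too few, and 48 is exactly 40 × 1.2. The protocol then claims something the design does not have: 40 evaluable patients after 20% drop-out.

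The second cohort makes this more than a rounding question. Both cohorts are given as 12 per group and 48 in total, so a reader will assume that they are protected alike. If the night-splint 48 is the number needed before drop-out, the two identical figures mean different things, and the night-splint primary comparison has no protection.

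**Working it through.** **Inputs.** From the dynamic Sample size section: α = 0.05, power 0.80, k = 4 groups, m = 2 measurements, correlation ρ = 0.6, 40 required, 20% margin, 48 enrolled. From the night-splint Sample size section: m = 3, ρ = 0.4, 48 patients. From section 4: cap 105. Assumption: the 25% effect size is Cohen's f = 0.25. The protocol does not name the measure, but this reading reproduces both cohort sizes.

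**Formula.** Repeated-measures ANOVA, within-between interaction, non-central F: λ = f²·N·m/(1 − ρ), df1 = (k − 1)(m − 1), df2 = (N − k)(m − 1).

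**Step 1: reproduce the 40.** With N = 40, λ = 0.0625 × 40 × 2/0.4 = 12.5, df = 3 and 36, and power is 81.2%. With N = 39 it is 79.97%. So 40 is the smallest number reaching 80%, which matches the protocol and leaves no slack. Other tests with the same inputs do not match: the within-factor test needs 28 and the four-group between-factor test needs 144.

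**Step 2: the margin in the dynamic cohort.**
- The protocol's route: 40 × 1.2 = 48.
- After 20% drop-out: 48 × 0.8 = 38.4, or 9.6 per group against the required 10.
- Drop-out that 48 tolerates: (48 − 40)/48 = 16.7%.
- Number that covers 20%: 40/0.8 = 50. Per group this is 12.5, so four equal groups need 13 each, 52 in total.
- Power at 38: λ = 0.0625 × 38 × 2/0.4 = 11.875, df = 3 and 34, power 78.7%.

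**Step 3: the night-splint 48.**
- N = 48: λ = 0.0625 × 48 × 3/0.6 = 15, df = 6 and 88, power 81.2%. The smallest N for 80% is 47, which rounds up to 48 for four equal groups.
- Could 48 be an inflated 40? Power at 40 is 71.5%, so 40 would not have met the target.
- After 20% drop-out: 48 × 0.8 = 38.4. At 38, λ = 0.0625 × 38 × 3/0.6 = 11.875, df = 6 and 68, power 68.6%.

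**Step 4: the cap.**

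| Dynamic | Night splints | Total | Within 105? |
|---|---|---|---|
| 48 (as stated) | 48 (as stated) | 96 | yes |
| 50 | 48 | 98 | yes |
| 52 | 48 | 100 | yes |
| 50 | 48/0.8 = 60 | 110 | no |

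The cap is passed only when a full 20% margin is given to both cohorts.

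**The case against.** The best defence is the wording. The protocol speaks of a margin for drop-out and states no expected drop-out rate. Read as adding 20% to 40, the sentence gives 48 with no slip. That explains how 48 arose, but it does not rescue the sentence: the margin is tied to drop-out, and nothing tells the reader that the tolerance it buys is 16.7%.

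The second defence is size, and it stands. The gap is 2 patients against 50, or 4 against 52, and power falls about one point below target in a calculation that rests on an assumed effect size and an assumed correlation. A reader might compute the chance that at least 40 of 48 remain under independent 20% drop-out, which is 36%, and conclude that the gap is large. That measure misleads: 50 enrolled gives only 58% on it, because inflation aims at the expected number remaining.

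A reader might also infer that the cap of 105 is wrong or cannot carry the margin. The protocol does not support this. The cap is a maximum and need not equal the sum of the cohorts. The only margin stated, that for the dynamic cohort, fits at 98 or 100. The total of 110 appears only after adding a night-splint margin that the protocol never claims. Section 3 also lists a seating-shell group with no stated size, so the two cohorts may not be all that the cap covers.

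Finally, the missing night-splint margin is a related but separate matter from the 1.2 against 1/0.8 slip. That is fair, and the 69% should not be used to raise the weight of the dynamic error.

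**Conclusion.** The point holds for the dynamic cohort and is minor there. The 48 enrolled cover 16.7% drop-out; at 20%, about 38 remain and power is about 79% against the 80% target. The shortfall in patients follows from the protocol's own 40, 48 and 20% alone. The power figures also assume f = 0.25 and the four-group interaction test, the one that reproduces the 40.

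The night-splint 48 carries no visible margin. It reproduces as a number before drop-out, and the 20% used for the other cohort would bring power to about 69%. This is an inference from the arithmetic, since the protocol does not say on which side of drop-out its 48 lies, and it sets no drop-out figure for that cohort.

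There is no error in the cap of 105.

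**What to change.** In the dynamic Sample size section, say either that 48 covers drop-out of 16.7%, or that at 20% drop-out about 38 patients are evaluable and power is about 79%. In the night-splint Sample size section, say that 48 is the number needed before drop-out and carries no margin, and give the consequence: about 38 patients and about 69% power if 20% are lost. Name the effect-size measure behind the 25%, so that both figures can be checked.

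This costs wording only; the stated protection becomes slightly less favourable for the dynamic cohort and clearly less favourable for night splints. If the sponsor prefers to keep the 20% claim for the dynamic cohort, 50 patients would meet it, or 52 in equal groups. That is 2 or 4 more than planned and stays within 105 alongside the 48 night-splint patients. The cap needs no change for this.
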